FSH ^f	X							Optional. See footnotes
TDM Test ^g	X							Optional. See footnotes
Diagnostic Test for SARS-CoV-2	X							Participants must have a negative SARS-CoV-2 PCR test result prior to Day 1, in accordance with site standard practices
Stool Collection								
For Clostridium difficile Testing (and stool infectious screen)	X						x ^h	Stool test results from anytime within 30 days prior to starting first dose of study intervention can be considered for screening process. Results must be documented, if obtained locally.

Table 2-1: Schedule of Activities for Year 1 (IM047029)

Procedure	Screening (Days -28 to -1)	Week 0 (Day 1)	Week 4 (Day 28)	Week 12 (Day 84)	Week 26 (Day 182)	Week 52 (Day 365)	Unscheduled ^a	Notes
Visit Window (± n Days)			7	7	7	14		
For Culture, Ova, and Parasites ⁱ	X							or stool PCR - see footnotes
Endoscopy and Biopsies^j								
Cohort 1 (Advanced Therapy-naïve Cohort)	X			X				Results from endoscopy (colonoscopy or sigmoidoscopy) performed within 60 days prior to first dose of study intervention may be considered for the screening process. Images must be documented to confirm severity. In the setting of historic (prior) endoscopy documentation, biopsy tissue will not be collected.
Cohort 2 (Advanced Therapy-exposed Cohort)	X				X			Results from endoscopy performed within 60 days prior to first dose, may be considered for the screening process. Images must be documented to confirm severity. In the setting of historic (prior) endoscopy documentation, biopsy tissue will not be collected.
Additional Efficacy Assessments^k								
Site Calculates Modified Mayo Score	X			X ^l	X ^m			Required for eligibility assessment

Table 2-1: Schedule of Activities for Year 1 (IM047029)

Procedure	Screening (Days -28 to -1)	Week 0 (Day 1)	Week 4 (Day 28)	Week 12 (Day 84)	Week 26 (Day 182)	Week 52 (Day 365)	Unscheduled ^a	Notes
Visit Window (± n Days)			7	7	7	14		
Baseline (prior to flare) SF	X							
PGA Collection	X	X	X	X	X	X		Physician-reported
RB Subscore	X	X	X	X	X	X		Recorded for 7 days prior to Day 1, daily for the first 12 weeks of the study, and 7 days prior to each study visit thereafter
SF Subscore	X	X	X	X	X	X		
HRQOLⁿ								
IBDQ		X	X	X	X	X		

Table 2-1: Schedule of Activities for Year 1 (IM047029)

Procedure	Screening (Days -28 to -1)	Week 0 (Day 1)	Week 4 (Day 28)	Week 12 (Day 84)	Week 26 (Day 182)	Week 52 (Day 365)	Unscheduled ^a	Notes
Visit Window (± n Days)		7	7	7	14			
Healthcare Resource Utilization^b								

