3.1 Study Rationale

This prospective, open-label, Phase 4 study is designed to explore the safety, efficacy, effects on quality of life (QOL), and biomarker response of ozanimod in participants with moderate to severely active UC in clinical practice.

The study population will be consistent with the product label, so that this study may generate data that are directly relevant to the labeled indication and that may be used to further inform the clinical use of ozanimod in this study population.

The study will include 2 cohorts:

- **Cohort 1:** Participants with moderate to severely active UC who have not been exposed to biologics or immunomodulators for the treatment of UC (ie, advanced therapy-naïve).
- **Cohort 2:** Participants with moderate to severely active UC who have been exposed to a single mechanism of action of biologics for the treatment of UC (ie, advanced therapy-exposed).

This study will generate additional data on the effect of ozanimod treatment, including (but not limited to) the following:

- Characterization of early response (improvement in signs and symptoms of UC within the first 4 weeks), including rectal bleeding (RB), stool frequency (SF), urgency, and abdominal symptoms.
- Characterization of the endoscopic and histologic response to ozanimod at Week 12 in an advanced therapy-naïve cohort.
- Characterization of the endoscopic and histologic response to ozanimod at Week 26 in an advanced therapy-exposed cohort.
- Characterization of the long-term safety of ozanimod over the duration of the study.
- Patient-reported outcome (PRO) measures, including impact on disease-specific QOL and symptoms, fatigue, patient satisfaction with treatment, and work productivity.
- Characterization of the effect of ozanimod treatment on biomarkers of disease activity used in clinical practice, [REDACTED]

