4 OBJECTIVES AND ENDPOINTS

The study objectives and endpoints are listed in the following 3 tables:

- Table 4-1: Objectives and endpoints that are specific to Cohort 1.
- [Table 4-2](#): Objectives and endpoints that are specific to Cohort 2.
- [Table 4-3](#): Objectives and endpoints that are common for both Cohort 1 and Cohort 2.

Additional endpoints and analyses will be described in the statistical analysis plan (SAP), the Endoscopy Image Review Charter, and/or the Histopathology Image Review Charter (as applicable). Selected endpoint definitions are provided in [APPENDIX 6](#).

Table 4-1: Objectives and Endpoints Specific to Advanced Therapy-naïve Cohort (Cohort 1)

Objectives	Endpoints
Primary 
• To explore the efficacy of ozanimod in inducing clinical response in the advanced therapy-naïve cohort.	Primary 
• Clinical response at Week 12, as measured by modified Mayo score.
Secondary 
• To explore the efficacy of ozanimod in the advanced therapy-naïve cohort.• To explore the effects of ozanimod on disease-specific HRQOL in the advanced therapy-naïve cohort.	Secondary 
• Clinical remission at Week 12, as measured by modified Mayo score.• Endoscopic response at Week 12.• Endoscopic improvement at Week 12.• Histological improvement at Week 12.• Change in the IBDQ total score from baseline to Week 12.• IBDQ response (change in total score [≥ 16 points] from baseline to Week 12).• IBDQ remission (total score [≥ 170 points]) at Week 12.

IBDQ, Inflammatory Bowel Disease Questionnaire.

Table 4-2: Objectives and Endpoints Specific to Advanced Therapy-exposed Cohort (Cohort 2)

Objectives	Endpoints
Primary 
To explore the efficacy of ozanimod in inducing clinical response in the advanced therapy-exposed cohort.	Primary 
Clinical response at Week 26, as measured by modified Mayo score.

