Secondary 
To explore the efficacy of ozanimod in the advanced therapy-exposed cohort.	Secondary 
Clinical remission at Week 26, as measured by modified Mayo score.Endoscopic response at Week 26.Endoscopic improvement at Week 26.Endoscopic remission at Week 26.Histological improvement at Week 26.Histological remission at Week 26.Change in the IBDQ total score from baseline to Week 26.IBDQ response (change in total score [\geq 16 points] from baseline to Week 26).IBDQ remission (total score [\geq 170 points]) at Week 26.Corticosteroid-free clinical remission at Week 26, as measured by modified Mayo score.HEMI at Week 26.

HEMI, histo-endoscopic mucosal improvement; IBDQ, Inflammatory Bowel Disease Questionnaire.

Table 4-3: Additional Objectives and Endpoints Common for both the Advanced Therapy-naïve Cohort (Cohort 1) and the Advanced Therapy-exposed Cohort (Cohort 2) after Week 26

Objectives	Endpoints

Secondary
 
• To explore the safety and tolerability of ozanimod in the advanced therapy-naïve cohort and the advanced therapy-exposed cohort.• To explore the long-term durability of response to ozanimod in the advanced therapy-naïve cohort and the advanced therapy-exposed cohort.	
Secondary
 
• Number and proportion of participants experiencing the following:
– AEs.– SAEs.– AEs and SAEs, including AEIs and other select AEs, leading to discontinuation from the study intervention and the study.– Clinical laboratory values.• Clinical remission by partial Mayo score at Weeks 52 and 104.• Corticosteroid-free clinical remission by partial Mayo score at Weeks 52 and 104.• Clinical response by partial Mayo score at Weeks 52 and 104.

Table 4-3: Additional Objectives and Endpoints Common for both the Advanced Therapy-naïve Cohort (Cohort 1) and the Advanced Therapy-exposed Cohort (Cohort 2) after Week 26

Objectives	Endpoints
AEI, adverse event of interest;	SAE, serious adverse event;

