6.1 Inclusion Criteria

Participants are eligible to be included in the study only if all of the following criteria apply:

1) Signed Written Informed Consent

- a) Participants must have signed and dated an Institutional Review Board (IRB)/Independent Ethics Committee (IEC)-approved written informed consent form (ICF) in accordance with regulatory, local, and institutional guidelines. This must be obtained before the performance of any protocol-related procedures that are not part of normal patient care.

2) Type of Participant and Target Disease Characteristics

- a) A diagnosis of UC, with signs and symptoms consistent with UC for at least 3 months prior to the first study intervention administration.
- b) Moderate to severely active UC disease activity, defined as a modified Mayo score of 4 through 9, inclusive, with the following minimum subscores:
 - i) An SF subscore ≥ 1 ,

AND

ii) An RB subscore ≥ 1 ,

AND

iii) An ES ≥ 2 (endoscopy performed within 60 days of the first study intervention administration).

- c) Must be up to date with screening for colorectal neoplasia and surveillance for dysplasia, according to local standard of care.
- d) Must have documentation of positive VZV IgG antibody status at screening or complete VZV vaccination prior to the first study intervention administration.
- e) Report of a previous colonoscopy that documents extent of disease (Note: If performed in the prior 60 days, this data may be used for study inclusion.)
- f) UC disease distribution (including ulcerative proctitis) extending proximal to the rectum (ie, approximately ≥ 5 cm from anal margin).

3) Age of Participant

- a) Participant must be over 18 years of age (or the legal age of consent in the jurisdiction in which the study is taking place) at the time of signing the informed consent.

4) Cohort 1 (Advanced Therapy-naïve Cohort): Disease Distribution and Prior UC Medication Exposure

In order to participate in Cohort 1, a participant must meet the eligibility criteria outlined in this inclusion criterion (IC) and must not meet the eligibility criteria outlined in IC 5.

- a) Participants must be naïve to 6-mercaptopurine/AZA and any biologics (see IC 5[a] for list) for any other medical indication, as well as UC.

5) Cohort 2 (Advanced Therapy-exposed Cohort): Disease Distribution and Prior UC Medication Exposure

In order to participate in Cohort 2, a participant must have failed only one mechanism of action of biologics.

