APPENDIX 6 SELECTED ENDPOINT DEFINITIONS

Clinical Response (modified Mayo score, primary endpoint)	Achieving the following changes from baseline in the modified Mayo score: 
• A decrease from baseline in the modified Mayo score ≥ 2 points, and• A decrease from baseline in the modified Mayo score $\geq 35\%$, and• A decrease from baseline in RB subscore ≥ 1 point or absolute RB subscore ≤ 1.
Clinical Remission (modified Mayo score)	A modified Mayo score with the following: 
• SF subscore ≤ 1, with ≥ 1 point decrease from baseline, and• RB subscore = 0, and• ES ≤ 1
Clinical Remission (partial Mayo)	Partial Mayo score ≤ 2.5
Endoscopic Response	A decrease from baseline of ≥ 1 point in Mayo ES
Endoscopic Improvement	Mayo ES ≤ 1

Endoscopic Remission		Mayo ES = 0
Histological Improvement	•	• Achieving a Geboes score < 3.1
Histologic Remission		Achieving Geboes score < 2
HEMI		Mayo ES \leq 1 and a Geboes score < 3.1
Corticosteroid-free Clinical Remission (modified Mayo score)		Clinical remission (by modified Mayo criteria), and no oral systemic steroid use in prior 90 days.
Corticosteroid-free Clinical Remission (partial Mayo score)		Clinical remission (by partial Mayo criteria), and no oral systemic steroid use in prior 90 days.

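### Histological improvement is scored as Geboes < 3.1 at the visit with no baseline condition, so the rate mixes participants who improved with any already below 3.1 before dosing

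*Combined protocol and SAP*

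**What the plan says.** Histological improvement is a secondary endpoint in both cohorts: "Histological improvement at Week 12" in Table 4-1 and "Histological improvement at Week 26" in Table 4-2. Its only definition is in Appendix 6: "Achieving a Geboes score < 3.1". Section 10.4.4 refers the reader to Table 10.4.3-1 for a description of every secondary endpoint, but that table, as supplied, has no row for this one. It therefore adds no baseline term.

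Entry is set on clinical and endoscopic activity. Section 6.1, criterion 2b, reads "Moderate to severely active UC disease activity, defined as a modified Mayo score of 4 through 9, inclusive, with the following minimum subscores". The subscores are stool frequency of at least 1, rectal bleeding of at least 1 and endoscopic subscore (ES) of at least 2. No inclusion or exclusion criterion mentions a Geboes score.

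Baseline histology will be missing for some participants. A screening endoscopy done up to 60 days before the first dose may be used, and Table 2-1 then states: "In the setting of historic (prior) endoscopy documentation, biopsy tissue will not be collected". The efficacy population in Section 10.3 is all treated participants in each cohort, so these participants stay in the denominator.

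**The concern.** The endpoint's name suggests a change, and Section 3.1 lists as a purpose of the study "Characterization of the endoscopic and histologic response to ozanimod at Week 12 in an advanced therapy-naïve cohort", with a parallel statement for Cohort 2 at Week 26. The scoring rule looks at one time point. A participant below 3.1 at screening and again at the visit counts as improved. So does one whose score rises between the two visits but stays under the cut.

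Endoscopic improvement (ES of 1 or less) has the same form but is protected, because entry requires ES of at least 2 and anyone meeting it must have fallen by at least 1 point. Histology has no such entry floor. There is also no control arm, so nothing offsets the share already below the cut at entry. That share raises the reported proportion, and a larger sample would not reduce it. As planned, the result cannot separate improvement from pre-existing status.

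**Working it through.** The plan states no expected rate, precision or sample size for histological improvement, so there is no figure of its own to reproduce.

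**Definitions side by side**

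| Endpoint | Rule | Does it guarantee a change from baseline? |
|---|---|---|
| Endoscopic response | "A decrease from baseline of ≥ 1 point in Mayo ES" | Yes, written in the rule |
| Endoscopic improvement | ES of 1 or less | Yes, through entry at ES of at least 2 |
| IBDQ response | Change of at least 16 points | Yes, written in the rule |
| Histological improvement | "Achieving a Geboes score < 3.1" | No |

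**Inputs for the illustration**
- *q*: share of treated participants below 3.1 at baseline. Not in the documents; assumed from 1% to 25%.
- *r*: proportion reaching a score below 3.1 among those at 3.1 or above at baseline. Not in the documents; assumed 30%, with 20% to 40% as a range.
- *s*: proportion of those below 3.1 at baseline who are still below it and are not removed as failures or missing. Not in the documents; assumed 90%, with 80% to 100% as a range.
- Planned treated numbers: 150 and 100 (Section 10.2).

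**Formulas**
- Reported rate = *q* × *s* + (1 − *q*) × *r*
- Excess over the rate in participants with active histology = *q* × (*s* − *r*)

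With *r* = 30% and *s* = 90%, the excess is 0.6 × *q*:

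| *q* | Reported rate | Excess over 30% |
|---|---|---|
| 1% | 0.009 + 0.297 = 30.6% | 0.6 points |
| 2% | 0.018 + 0.294 = 31.2% | 1.2 points |
| 5% | 0.045 + 0.285 = 33.0% | 3 points |
| 10% | 0.090 + 0.270 = 36.0% | 6 points |
| 25% | 0.225 + 0.225 = 45.0% | 15 points |

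Varying *r* over 20% to 40% and *s* over 80% to 100%, the excess runs from *q* × (0.8 − 0.4) to *q* × (1.0 − 0.2). That is 2 to 4 points at *q* = 5%, 4 to 8 at 10% and 8 to 16 at 20%.

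**Scale.** Each participant below 3.1 at baseline who stays there adds 1/150 = 0.67 points in Cohort 1 or 1/100 = 1.0 point in Cohort 2. At an observed rate of 30%, the Clopper-Pearson 95% half-width is 7.6 points for 45/150 and 9.4 points for 30/100. The excess is therefore negligible at *q* = 1% and approaches the half-width at *q* = 10%.

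**The case against.** The strongest reply is that the protocol uses its terms consistently. For endoscopy, response is a change and improvement is a state at the visit; histological improvement follows the second pattern. IBDQ remission (170 points or more) also has no baseline condition and no entry threshold. This stands as a defence of the naming. It does not answer the substance, because the endoscopic state implies a change through the entry rule and the histologic state does not.

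Second, entry at ES of at least 2 with rectal bleeding may make a baseline score below 3.1 uncommon. That is plausible, and the documents cannot settle it. It is why the size must be left open.

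Third, not everyone below 3.1 at entry is counted. The treatment-failure rules in Section 7.7.2.1 apply to all efficacy endpoints, Section 10.3 treats discontinuation or prohibited medication before the primary visit as non-response for the primary estimand, and Section 10.4.3 imputes missing data as non-response. This also stands, but none of these rules removes a stable completer.

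Fourth, restricting the endpoint to participants with a baseline biopsy would leave the all-treated population and select by screening route. That is a fair argument against replacing the definition, and the fix below does not replace it.

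Fifth, Section 10.4.4 leaves analysis details to the SAP, which might report results by baseline histology. The supplied text contains no such provision.

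A reader might also infer that histologic remission (Geboes < 2, Cohort 2) has the same fault. The documents do not support that, since remission names a state and claims no change. HEMI, also in Cohort 2, uses the same Geboes cut, but its endoscopic half does force a change.

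**Conclusion.** The point holds as a matter of definition. Histological improvement has no baseline condition, entry sets no histology level, and participants screened on a historic endoscopy have no baseline score to compare with. The reported rate therefore cannot distinguish improvement from a score already below 3.1.

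Its size is unknown. The excess of 0.6 points at a 1% baseline share and 6 points at 10% rests wholly on the assumed 30% and 90%, and the baseline share is itself an assumption. A reader might infer a bias of 3 to 15 points from the 5% to 25% rows above, but nothing in the documents excludes a share below 5%, or one near zero. A reader might also infer that the endpoint is uninformative or would be presented as a proven drug effect. The study is descriptive with no hypothesis testing (Section 10.1), and the all-treated proportion below 3.1 is a valid description of status at the visit.

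This is a worthwhile, inexpensive improvement to one secondary endpoint in each cohort. The primary endpoints are not affected.

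**What to change.** 1. Keep the all-treated proportion with Geboes < 3.1 at Week 12 or Week 26. In Appendix 6 and the SAP, label it as a histologic status at the visit.
2. Report beside it, by cohort, the proportion below 3.1 at baseline among those with a baseline biopsy, and the number treated with no baseline biopsy.
3. Prespecify a supplementary analysis: the proportion reaching Geboes < 3.1 among treated participants whose baseline biopsy scored 3.1 or above, with a Clopper-Pearson interval and with non-responder imputation and the treatment-failure rules unchanged. Base any statement about histologic improvement or response on this analysis.
4. Add the missing row for histological improvement to Table 10.4.3-1.
5. Write this in before the first planned analysis in Section 10.5, not merely before database lock.

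Leave histologic remission as it is.

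The cost is wording and a few table cells; no biopsy or visit is added. The supplementary analysis has a smaller denominator, because it omits participants screened on a historic endoscopy and those below 3.1 at baseline. How many is not known. If half of Cohort 1 were lost (an assumption), 23/75 gives a 95% interval of 20.5% to 42.4%, a half-width of 10.9 points against 7.6 for 45/150. For half of Cohort 2, 15/50 gives 17.9% to 44.6%, a half-width of 13.4 points against 9.4 for 30/100. That loss is the reason to keep the all-treated proportion and make the restricted analysis supplementary.
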